# **10 STUDY MANAGEMENT**

## **10.1 Compliance**

### **10.1.1 Compliance with the Protocol and Protocol Revisions**

The investigator should not implement any deviation or change to the protocol without prior review and documented approval/favorable opinion of an amendment from the IRB/IEC (and if applicable, also by local health authority) except where necessary to eliminate an immediate hazard(s) to study participants.

If a deviation or change to a protocol is implemented to eliminate an immediate hazard(s) prior to obtaining relevant approval/favorable opinion(s), the deviation or change will be submitted as soon as possible to:

- IRB/IEC
- Regulatory Authority(ies), if applicable by local regulations per national requirements

Documentation of approval/favorable opinion signed by the chairperson or designee of the IRB(s)/IEC(s) and if applicable, also by local health authority, must be sent to the Study Sponsor, Moffitt Cancer Center through the MCRN Coordinating Center.

If an amendment substantially alters the study design or increases the potential risk to the participant: (1) the consent form must be revised and submitted to the IRB(s)/IEC(s) for review and approval/favorable opinion; (2) the revised form must be used to obtain consent from participants currently enrolled in the study if they are affected by the amendment; and (3) the new form must be used to obtain consent from new participants prior to enrollment.

If the revision is done via an administrative letter, investigators must inform their IRB(s)/IEC(s).

### **10.1.2 Monitoring**

Regulatory documents and case report forms will be monitored internally according to Moffitt Cancer Center Monitoring Policies. Monitoring will be performed regularly to verify data is accurate, complete, and verifiable from source documents; and the conduct of the trial is in compliance with the currently approved protocol/amendments, Good Clinical Practice (GCP), and applicable regulatory requirements.

### **10.1.3 Source Documentation**

The Investigator is responsible for ensuring that the source data are accurate, legible, contemporaneous, original and attributable, whether the data are hand-written on paper or entered electronically. If source data are created (first entered), modified, maintained, archived, retrieved, or transmitted electronically via computerized systems (and/or any other kind of electronic devices) as part of regulated clinical trial activities, such systems must be compliant with all applicable laws and regulations governing use of electronic records and/or electronic

signatures. Such systems may include, but are not limited to, electronic medical/health records (EMRs/EHRs), adverse event tracking/reporting, protocol required assessments, and/or drug accountability records).

When paper records from such systems are used in place of electronic format to perform regulated activities, such paper records should be certified copies. A certified copy consists of a copy of original information that has been verified, as indicated by a dated signature, as an exact copy having all of the same attributes and information as the original.

## **10.2Records**

### **10.2.1Records Retention**

The Investigator must ensure that the records and documents pertaining to the conduct of the study and the distribution of the study drug, that is copies of CRFs and source documents (original documents, data, and records [e.g., hospital records; clinical and office charts; laboratory notes; memoranda; participant's diaries or evaluation checklists; SAE reports, pharmacy dispensing records; recorded data from automated instruments; copies or transcriptions certified after verification as being accurate copies; microfiches; photographic negatives, microfilm, or magnetic media; x-rays; participant files; and records kept at the pharmacy, at the laboratories, and at medico-technical departments involved in the clinical study; documents regarding patient treatment and study drug accountability; original signed informed consents, etc.]) be retained by the Investigator for as long as needed to comply with national and international regulations (generally 2 years after discontinuing clinical development or after the last marketing approval). The Investigator agrees to adhere to the document/records retention procedures by signing the protocol.

### **10.2.2Study Drug Records**

Records for IP (whether supplied by BMS, its vendors, or the site) must substantiate IP integrity and traceability from receipt, preparation, administration, and through destruction or return. Records must be made available for review at the request of BMS/designee or a Health Authority. Moffitt will provide forms to facilitate inventory control if the investigational site does not have an established system that meets these requirements.

### **10.2.3Case Report Forms**

Data will be captured in Oncore, Moffitt's Clinical Trials Database.

An investigator is required to prepare and maintain adequate and accurate case histories designed to record all observations and other data pertinent to the investigation on each individual treated in the investigation. Data that are derived from source documents and reported on the CRF must be consistent with the source documents or the discrepancies must be explained. Additional clinical information may be collected and analyzed in an effort to enhance understanding of product safety. CRFs may be requested for AEs and/or laboratory abnormalities that are reported or identified during the course of the study.

The confidentiality of records that could identify participants must be protected, respecting the privacy and confidentiality rules in accordance with the applicable regulatory requirements.

## 10.3 Clinical Study Report and Publications

The study of these patients and results of all laboratory studies are considered private and confidential. The progress and results of this study will not be presented without approval by the principal investigator.

Any publications or abstracts arising from this study must adhere to the publication requirements set forth in the clinical trial agreement (CTA) governing participation in the study. These requirements include, but are not limited to, submitting proposed publications to BMS at the earliest practicable time prior to submission or presentation and otherwise within the time period set forth in the CTA.

## 11 LIST OF ABBREVIATIONS

Term	Definition
AE	Adverse event
ALT	Alanine aminotransferase
ANC	Absolute neutrophil count
AIDS	Acquired immunodeficiency syndrome
aPTT	Activated partial thromboplastin time
AST	Aspartate aminotransferase
AT	Amino transaminases
 HCG	beta-human chorionic gonadotrophin
BID,bid	Bis in die, twice daily
BMS	Bristol-Myers Squibb
BP	Blood pressure

BUN	Blood urea nitrogen
C	Celsius
Ca++	Calcium
CBC	Complete blood count
CFR	Code of Federal Regulations
CI	Confidence interval
C1-	Chloride
CLcr	Creatinine clearance
Cm	Centimeter
CNS	Central nervous system
CRF	Case Report Form, paper or electronic
CTLA-4	Cytotoxic t lymphocyte-associated antigen 4
dL	Deciliter
ECG	Electrocardiogram
ECOG	Eastern Cooperative Oncology Group
eCRF	Electronic Case Report Form
ED-SCLC	Extensive disease-small cell lung cancer
Eg	Exempli gratia(for example)

FDA	Food and Drug Administration
FISH	Fluorescent in situ hybridization
FSH	Follicle stimulating hormone
G	Gram
GCP	Good Clinical Practice
GGT	gamma-glutamyltransferase
GFR	Glomerular filtration rate
H	hour
HbsAg	Hepatitis B surface antigen
HBV	Hepatitis B virus
HCV	Hepatitis C virus
HCO3-	bicarbonate
HIV	Human Immunodeficiency Virus
HR	Heart rate
HRT	Hormone replacement therapy
ICD	Immunogenic Cell Death
ICH	International Conference on Harmonization
Ie id	Est (that is)

IEC	Independent Ethics Committee
IMP	Investigational medicinal products
IND	Investigational New Drug Exemption
IRB	Institutional Review Board
IU	International Unit
IU/L	International unit per liter
IU/mL	International unit per milliliter
IVRS	Interactive voice response system
IV	intravenous
K +	potassium
Kg	Kilogram
KM	Kaplan-meier
L	Liter
LAM	Lactation amenorrhea method
LDH	Lactate dehydrogenase
mAB	Monoclonal antibody
Mg	Milligram
Mg ++	magnesium

Min	Minute
mL	Milliliter
mmHg	Millimeters of mercury
$\mu$ g	Microgram
N	Number of subjects or observations
Na +	Sodium
N/A	Not applicable
NE	Not evaluable
Ng	Nanogram
NCCN	National Comprehensive Cancer Network
NIMP	non-investigational medicinal products
NSCLC	Non small cell lung cancer
ORR	Overall response rate
OS	Overall survival
PD	Progressive disease
PD	Pharmacodynamics
PD-1	ProgrammedDeath-1
PD-L1	Programmeddeath-ligand1

PD-L2	Programmed death-ligand2
PFS	progression-free survival
PR	Partial response
PK	Pharmacokinetics
PT	Prothrombin time
RCC	Renal cell carcinoma
RECIST1.1	Response evaluation criteria in solid tumors version 1.1
RBC	Red blood cell
RT	Radiation Therapy
SAE	Serious adverse event
SCLC	Small cell lung cancer
SD	Standard deviation
SD	Stable disease
SOP	Standard Operating Procedures
T	Temperature
T	Time
TILs	Tumor infiltrating lymphocytes
TTR	Thoracic radiation therapy

TSH	Thyroid stimulating hormone
ULN	Upper limit of normal
WBC	White blood cell
WOCBP	Women of childbearing potential

# 13 APPENDIX 1: STUDY CALENDAR

	Screening A	W-3	W-2	W-1	W1 B	W2 C	W3	W4 D	W5	W6	W7	W8	W9	W10	W11	W12	W13	W14	W15	W16	W17	W18	W19 E	W20	W21	W22	W23	W24	W25	W26	W27 F	Follow Up G	Survival Follow up H
Informed Consent	X																																
Inclusion/Exclusion Criteria	X																																
Medical History	X																																
Physical Examination	X				X	X		X		X		X		X		X		X		X		X		X		X		X	X	X			
Adverse Events Assessment	X	X	X	X	X	X	X	X	X	X	X	X	X	X	X	X	X	X	X	X	X	X	X	X	X	X	X	X					
Concomitant Medication Collection	X																																
Review of Concomitant Medications					X	X		X		X		X		X		X		X		X		X		X		X		X	X	X			
Screening Laboratory Tests	X																																
Extended Laboratory Tests					X	X		X		X		X		X		X		X		X		X		X		X		X	X	X			
Thyroid Function Testing	X				X			X				X										X				X		X	X	X			
ECG	X																																
Pregnancy Test	X				X			X		X		X		X		X		X		X		X		X		X		X	X	X			
Simulation for Thoracic Radiation Therapy					X O																												
CT Chest w/ IV contrast I	X							X				X				X						X								X			
CT Abdomen w/ IV and oral contrast I	X							X				X				X						X								X			
CT Pelvis w/ IV and oral contrast K	X							X				X				X						X								X			
MRI Brain w/ IV contrast L	X											X				X														X			
Attempt collection of diagnostic FFPE tumor tissue M	X																																
Peripheral Blood for Biomarkers N	X				X	X		X		X		X		X		X		X		X		X		X		X		X	X	X			
Administer Thoracic Radiation Therapy					XXXX X	XXXX X																											
Administer Ipilimumab 3mg/kg								X P		X		X		X		X		X		X		X		X		X		X					
Administer Nivolumab 1mg/kg								X		X		X		X		X		X		X		X		X		X		X					
Administer Nivolumab 480mg																						X				X		X		X			

A Not more than 28 days before initiation of RT. See Table 7.1-1 for details of screening procedures.

B Within 72 hours prior to initiation of RT. See Table 7.1-2 for details of thoracic RT schedule.

C Within 72 hours after completing RT. See Table 7.1-2 for details of thoracic RT schedule.

D See Table 7.1-3 for details of combined ipilimumab and nivolumab treatment schedule.

E See Table 7.1-4 for details of nivolumab alone treatment schedule.

F See Table 7.1-4 for detailed instructions related to ongoing assessments with nivolumab maintenance therapy

G See Table 7.1-5 for details of follow up after discontinuation of study therapy.

H See Table 7.1-5 for details of survival follow up visits.

K Required only if patient has known history of pelvic metastases

L CT brain w/ contrast acceptable

M For exploratory biomarker evaluation (prefer surgical specimen or core biopsy tissue, FNA also acceptable)

N See Table 7.5-1 for details of peripheral blood collection for biomarkers

O Anytime within 28 days before initiation of RT

[figure not shown]
P Must start more than 14 days but less than 28 days after completion of RT

## 14 APPENDIX 2: MANAGEMENT ALGORITHMS FOR IMMUNE ADVERSE EVENTS

These general guidelines constitute guidance to the Investigator and may be supplemented by discussions with the Principal Investigator.. The guidance applies to all immuno-oncology (I-O) agents and regimens. A general principle is that differential diagnoses should be diligently evaluated according to standard medical practice. Non-inflammatory etiologies should be considered and appropriately treated. Corticosteroids are a primary therapy for immuno-oncology drug-related adverse events. The oral equivalent of the recommended IV doses may be considered for ambulatory patients with low-grade toxicity. The lower bioavailability of oral corticosteroids should be taken into account when switching to the equivalent dose of oral corticosteroids. Consultation with a medical or surgical specialist, especially prior to an invasive diagnostic or therapeutic procedure, is recommended. The frequency and severity of the related adverse events covered by these algorithms will depend on the immuno-oncology agent or regimen being used.

# GI Adverse Event Management Algorithm

Rule out non-inflammatory causes. If non-inflammatory cause is identified, treat accordingly and continue I-O therapy. Opiates/narcotics may mask symptoms of perforation. Infliximab should not be used in cases of perforation or sepsis.

[figure not shown]

Patients on IV steroids may be switched to an equivalent dose of oral corticosteroids (e.g. prednisone) at start of tapering or earlier, once sustained clinical improvement is observed. Lower bioavailability of oral corticosteroids should be taken into account when switching to the equivalent dose of oral corticosteroids.

Updated 05-Jul-2016

# Renal Adverse Event Management Algorithm

[figure not shown]
Rule out non-inflammatory causes. If non-inflammatory cause, treat accordingly and continue I-O therapy

Patients on IV steroids may be switched to an equivalent dose of oral corticosteroids (e.g. prednisone) at start of tapering or earlier, once sustained clinical improvement is observed. Lower bioavailability of oral corticosteroids should be taken into account when switching to the equivalent dose of oral corticosteroids.

# Pulmonary Adverse Event Management Algorithm

[figure not shown]
Rule out non-inflammatory causes. If non-inflammatory cause, treat accordingly and continue I-O therapy. Evaluate with imaging and pulmonary consultation.

Patients on IV steroids may be switched to an equivalent dose of oral corticosteroids (e.g. prednisone) at start of tapering or earlier, once sustained clinical improvement is observed. Lower bioavailability of oral corticosteroids should be taken into account when switching to the equivalent dose of oral corticosteroids.

# Hepatic Adverse Event Management Algorithm

Rule out non-inflammatory causes. If non-inflammatory cause, treat accordingly and continue I-O therapy. Consider imaging for obstruction.

[figure not shown]
Patients on IV steroids may be switched to an equivalent dose of oral corticosteroids (e.g. prednisone) at start of tapering or earlier, once sustained clinical improvement is observed. Lower bioavailability of oral corticosteroids should be taken into account when switching to the equivalent dose of oral corticosteroids.

\*I-O therapy may be delayed rather than discontinued if AST/ALT  $\leq$  8 x ULN or T.bili  $\leq$  5 x ULN.

\*\*The recommended starting dose for grade 4 hepatitis is 2 mg/kg/day methylprednisolone IV.

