## **4.6 Discontinuation of Participants Following Any Treatment with Thoracic Radiation Therapy or Study Drug(s)**

Participants MUST discontinue investigational product (and non-investigational product at the discretion of the investigator) for any of the following reasons:

- Disease progression as assessed by RECIST 1.1 criteria, unless the participant meets criteria for treatment beyond progression (Section 6.5.5)
- Participant requests to stop study treatment
- Any clinical adverse event (AE), laboratory abnormality, or intercurrent illness that, in the opinion of the investigator, indicates that continued participation in the study is not in the best interest of the participant
- Discontinuation of study support by Bristol-Myers Squibb (BMS)
- Loss of ability to freely provide consent through imprisonment or involuntarily incarceration for treatment of either a psychiatric or physical (e.g., infectious disease) illness
- Additional protocol-specified reasons for discontinuation, as described in Section 6.5.3.4

In the case of pregnancy, the investigator must immediately notify the primary investigator or designee of this event. In most cases, study drug(s) will be permanently discontinued in an appropriate manner. If the investigator determines a possible favorable benefit/risk ratio that warrants continuation of study drug(s), a discussion between the primary investigator or designee, the IRB, and the Sponsor or designee must occur. All participants who discontinue study drug(s) should comply with protocol specified follow-up procedures as outlined in Section 7. The only exception to this requirement is when a participant withdraws consent for all study procedures including post-treatment study follow-up or loses the ability to consent freely (ie, is imprisoned or involuntarily incarcerated for the treatment of either a psychiatric or physical illness).

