## 6.5 Selection and Timing of Dose for Each Participant

The dosing schedules are detailed in Table 6.5-1.

Table 6.5-1. Dosing Schedule (Cycles 1-3)		
Cycles 1 and 2 (42-day [6 week] cycles)		Cycle 3 (28-day [4 week] cycles)
Day 1	Day 22	Day 1
1 mg/kg Nivolumab (diluted to 100 mL)	1 mg/kg Nivolumab (diluted to 100 mL)	480 mg Nivolumab (48 mL diluted 100 mL)
3 mg/kg Ipilimumab (diluted to 100 mL)	3 mg/kg Ipilimumab (diluted to 100 mL)	

For participants weighing < 35 kg, nivolumab and ipilimumab must be diluted to 50 mL in 0.9% sodium chloride or 5% dextrose solution.

All participants will be monitored continuously for adverse events (AEs) while on study treatment. Treatment modifications (eg, dose delay or discontinuation) will be based on specific laboratory and AE criteria, as described in Sections 6.5.3.

When study drugs (ipilimumab or nivolumab) are to be administered on the same day, separate infusion bags and filters must be used for each infusion. Nivolumab is to be administered first. The second infusion will always be the ipilimumab study drug and will start no sooner than 30 minutes after completion of the nivolumab infusion.

Ipilimumab must be diluted to 100 mL in 0.9% sodium chloride solution or 5% dextrose solution. Nivolumab must be diluted to 100 mL 0.9% sodium chloride solution or 5% dextrose solution. For weight-based dosing, if the participants weight on the day of dosing differs by > 10% from the weight used to calculate the dose, the dose must be recalculated. All doses should be rounded up or to the nearest milligram per institutional standard. There will be no dose modifications allowed.

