#### **6.5.3.4 Discontinuation Criteria**

Treatment with study therapy should be permanently discontinued for the following:

- Any Grade 2 drug-related uveitis or eye pain or blurred vision that does not respond to topical therapy and does not improve to Grade 1 severity within the re-treatment period OR requires systemic treatment
- Any Grade 3 non-skin, drug-related AE lasting > 7 days, with the following exceptions:
  - Grade 3 drug-related uveitis, pneumonitis, bronchospasm, neurologic toxicity, hypersensitivity reaction, or infusion reaction of any duration requires discontinuation
  - Grade 3 drug-related laboratory abnormalities do not require treatment discontinuation except:
    - ◆ Grade 3 drug-related thrombocytopenia > 7 days or associated with bleeding requires discontinuation
    - ◆ Any drug-related liver function test (LFT) abnormality that meets the following criteria require discontinuation:
      - AST or ALT > 8 x ULN
      - Total bilirubin > 5 x ULN
      - Concurrent AST or ALT > 3 x ULN and total bilirubin > 2 x ULN
- Any Grade 4 drug-related AE or laboratory abnormality, except for the following events which do not require discontinuation:
  - Grade 4 neutropenia  $\leq$  7 days
  - Grade 4 lymphopenia or leukopenia
  - Isolated Grade 4 electrolyte imbalances/abnormalities that are not associated with clinical sequelae and are corrected with supplementation/appropriate management within 72 hours of their onset
  - Grade 4 amylase or lipase abnormalities that are not associated with symptoms or clinical manifestations, or radiographic signs of pancreatitis. It is recommended to consult with the Principal Investigator for Grade 4 amylase or lipase abnormalities
  - For Grade 4 endocrinopathy AEs such as adrenal insufficiency, ACTH deficiency, hyper or hypothyroidosis, or glucose intolerance, which resolve or are adequately controlled with physiologic hormone replacement (steroids, thyroid hormones) or glucose controlling agents, respectively, retreatment can be considered after discussion with the Principal Investigator
- Any dosing interruption lasting > 6 weeks from the last dose with the following exceptions:

- Dosing interruptions to allow for prolonged steroid tapers to manage drug-related AEs are allowed. Prior to re-initiating treatment in a participant with a dosing interruption lasting > 6 weeks from the last dose, the Principal Investigator must be consulted

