#### **6.5.4 Management Algorithms for Immuno-Oncology Agents**

Immuno-oncology agents are associated with AEs that can differ in severity and duration from AEs caused by other therapeutic classes. Nivolumab and ipilimumab are considered immuno-oncology agents in this protocol. Early recognition and management of AEs associated with immuno-oncology agents may mitigate severe toxicity. Management algorithms have been developed to assist investigators in assessing and managing the following groups of AEs:

- Gastrointestinal
- Renal
- Pulmonary
- Hepatic
- Endocrinopathies
- Skin
- Neurological

The recommendation is to follow the nivolumab algorithms for immune-oncology agents (I-O) in order to standardize the safety management across the study.

The algorithms are found in the Nivolumab Investigator Brochure and Appendix 2 of this protocol.

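### The Appendix 2 hepatic footnote, on its own text, allows delay at liver values where Section 6.5.3.4 requires permanent discontinuation; this is a minor inconsistency, because 6.5.3.4 governs

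*Combined protocol and SAP*

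**What the plan says.** Section 6.5.3.4 sets the stop rule for liver tests: "Any drug-related liver function test (LFT) abnormality that meets the following criteria require discontinuation". Three criteria follow: AST or ALT above 8 x ULN; total bilirubin above 5 x ULN; and "Concurrent AST or ALT > 3 x ULN and total bilirubin > 2 x ULN". Any one of them is enough, and the discontinuation is permanent.

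Two other sections give that list its force. Section 6.5 says "Treatment modifications (eg, dose delay or discontinuation) will be based on specific laboratory and AE criteria, as described in Sections 6.5.3". Section 4.6 includes, among the reasons for which a participant must stop investigational product, "Additional protocol-specified reasons for discontinuation, as described in Section 6.5.3.4".

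The hepatic footnote in Appendix 2 reads differently: "I-O therapy may be delayed rather than discontinued if AST/ALT" is at most 8 x ULN or total bilirubin is at most 5 x ULN. It makes no exception for a concurrent elevation.

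On the standing of the algorithms, Appendix 2 opens with "These general guidelines constitute guidance to the Investigator and may be supplemented by discussions with the Principal Investigator". Section 6.5.4 says "The recommendation is to follow the nivolumab algorithms for immune-oncology agents (I-O) in order to standardize the safety management across the study", and adds "The algorithms are found in the Nivolumab Investigator Brochure and Appendix 2 of this protocol".

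**The concern.** The footnote repeats two of the three liver limits in 6.5.3.4 and drops the third. It also joins the two it keeps with 'or', although under 6.5.3.4 exceeding either one alone is enough to stop. Read by itself, it permits delay for some patients whom the binding section says must stop for good, so the mismatch is in the less safe direction.

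Delay and discontinuation have different consequences. Under Section 6.5.3.3 a delayed patient may generally resume once the event has settled to Grade 1 or baseline. Under 6.5.3.4 the patient does not resume. The footnote does not authorise resumption, but classing the event as a delay puts the patient on the path where resumption is considered.

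The omitted finding matters by the protocol's own standard. Section 8.6 uses the same thresholds (above 3 x for transaminases, above 2 x for bilirubin), with further conditions, to define potential drug-induced liver injury. Section 9.2.1 foresees up to five sites besides the lead institution, and 6.5.4 points them all to these algorithms without saying which text prevails.

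**Working it through.** The plan gives no figure to reproduce here. The check sets two written rules side by side. Let A be AST or ALT and B be total bilirubin, both in multiples of ULN, for a drug-related abnormality.

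- Section 6.5.3.4, stop if: A > 8, or B > 5, or (A > 3 and B > 2).
- Footnote read literally, delay allowed if: A ≤ 8 or B ≤ 5.
- Footnote read strictly, delay allowed if: A ≤ 8 and B ≤ 5.
- Proposed footnote, delay allowed if: A ≤ 8 and B ≤ 5 and not (A > 3 and B > 2).

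A conflict is a point where 6.5.3.4 requires a stop and the footnote allows delay. Six illustrative cases:

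| A / B (x ULN) | 6.5.3.4 | Literal 'or' | Strict 'and' | Proposed |
|---|---|---|---|---|
| 4 / 1 | no stop | delay | delay | delay |
| 4 / 3 | stop | delay (conflict) | delay (conflict) | no delay |
| 8 / 5 | stop | delay (conflict) | delay (conflict) | no delay |
| 10 / 1 | stop | delay (conflict) | no delay | no delay |
| 2 / 6 | stop | delay (conflict) | no delay | no delay |
| 10 / 6 | stop | no delay | no delay | no delay |

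Conflicts: 4 of 6 under the literal reading, 2 of 6 under the strict reading, 0 of 6 with the proposed wording.

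In general:

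1. Under the strict reading the conflict is exactly the box 3 < A ≤ 8 with 2 < B ≤ 5. That is the concurrent criterion less the part already stopped by a single limit.
2. The literal reading keeps that box and adds two regions: A > 8 with B ≤ 5, and B > 5 with A ≤ 8. Delay is then refused only when both single limits are exceeded.
3. The proposed condition is the exact negation of the 6.5.3.4 rule, so it leaves no conflict and adds no restriction beyond 6.5.3.4.

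As a check on the logic only, take a grid with A from 0 to 20 and B from 0 to 10 in steps of 0.1: 201 × 101 = 20,301 points.

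- Stop points: A > 8 gives 120 × 101 = 12,120. A ≤ 8 with B > 5 gives 81 × 50 = 4,050. The concurrent box gives 50 × 30 = 1,500. The total is 17,670.
- Conflicts, strict reading: 1,500.
- Conflicts, literal reading: 17,670 less the 120 × 50 = 6,000 points where delay is refused, which is 11,670.
- Conflicts, proposed wording: 0. Points where it refuses delay but 6.5.3.4 does not require a stop: 0.

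These counts depend on the chosen axes and say nothing about how often patients would have such values.

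**The case against.** The strongest objection is that the footnote hangs on a flowchart that is not shown. Where its asterisk sits decides which grade or laboratory range it qualifies, and the figure may itself carry the concurrent criterion. This stands as a limit. A reader might infer that the recommended hepatic guidance as a whole permits delay where the protocol forbids it, but the documents do not support that. Only the footnote's wording can be assessed, and the figure may narrow the conflict.

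Second, the binding rule is already clear. Section 4.6 makes the 6.5.3.4 criteria mandatory, Section 6.5 bases delay and discontinuation on 6.5.3, Appendix 2 calls itself guidance, and the footnote is permissive. An investigator who follows 6.5.3.4 breaches nothing in the appendix. This also stands, and it rules out the inference that the plan lacks a stop rule for concurrent elevation. It does not reconcile the two texts.

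Third, delay is not re-dosing. Section 6.5.3.3 governs resumption separately, and Section 6.5.3.1 leaves discontinuation open to the treating physician. A reader might infer that patients would be re-treated in error. Nothing in the documents shows this.

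Fourth, there are backstops. Values meeting all the conditions of Section 8.6 are handled as serious adverse events, reported within 24 hours under Section 8.1.1, and the monitoring committee reviews adverse events monthly (Section 8.8). Section 9.4.1 counts transaminases above 8 x ULN or bilirubin above 5 x ULN within the 13-week window as unacceptable toxicity, which feeds the stopping rules in Sections 4.1 and 9.1. These lower the stakes, but they act after the event and leave the wording as it is. Section 9.4.1 also does not name the concurrent finding, although such an event could count under its other items.

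Finally, the literal 'or' may be no more than loose drafting. That is plausible, and it is why the firm part of the finding is the box that remains under the strict reading.

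**Conclusion.** The point holds as a minor internal inconsistency in safety guidance. The footnote's text allows delay where 6.5.3.4 requires permanent discontinuation. Under either reading of 'or' this covers AST/ALT above 3 and up to 8 x ULN together with bilirubin above 2 and up to 5 x ULN. Under the literal reading it also covers cases where just one of the two single limits is exceeded.

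This rests on three assumptions: that the abnormality is drug-related; that the lead-in to the liver criteria in 6.5.3.4 means any such abnormality, as it says; and that the unseen flowchart does not already confine the footnote. The documents give no frequency for these values and none is assumed. The primary endpoint, the sample size and the decision rules are untouched.

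**What to change.** Make two wording changes in the next amendment, with a short memo to sites.

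1. Add to Section 6.5.4: *Where Appendix 2 or the Investigator Brochure copy of the algorithm differs from Section 6.5.3.4, Section 6.5.3.4 prevails.*
2. After checking the flowchart and the place of the asterisk, reword the footnote so that therapy *may be delayed rather than discontinued only if AST/ALT ≤ 8 x ULN and T.bili ≤ 5 x ULN and there is no concurrent AST/ALT > 3 x ULN with T.bili > 2 x ULN*.

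The first change settles precedence even if the flowchart turns out to limit the footnote. The second brings the footnote into line with 6.5.3.4. Neither adds visits, tests or patients, and no design figure changes. The one small drawback is that the footnote may then differ from the brochure copy of the algorithm, which is not among the documents; the precedence sentence covers that.
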